As already mentioned, the goal of this study is to investigate the "low LV mass phenotype" in patients with RA and its contributors in an attempt to elucidate the pathophysiology pathways that may connect RA with alterations in the myocardium and the evolution to heart failure. 3D-Echo will be used to measure the LV mass. Cardiac PET-CT imaging will be used to evaluate myocardial function (cardiac output, ejection fraction), microvasculature function (myocardial perfusion) and myocardial inflammation (F18-FDG uptake).

The research questions to be addressed with the study visit I are the following:

- i) Are anti-CCP antibodies or other RA-specific characteristics (e.g., disease duration, activity, severity) associated with lower LV mass (or other LV parameters of structure/function)?
- ii) What is the prevalence, the degree and correlates of microvascular dysfunction in RA? Is it associated with low LV mass or reduced global or regional contractility? Is it associated with systemic, articular and/or myocardial inflammation?
- iii) What are the prevalence, patterns, distribution and severity of inflammation as measured by F18-FDG uptake in myocardial PET imaging? Are intensity and/or distribution of F18-FDG uptake correlated with low LV mass or global or regional contractility? Does the severity/distribution of F18-FDG uptake correlate with levels of systemic and/or articular inflammation?

For the second aim of this study the goal is to evaluate the effect of TNF inhibitors on the myocardium. For the 50 patients undergoing randomization and the controls the questions to be addressed will be the following:

- i) Are global measures of LV structure (e.g., mass) or contractility (e.g., ejection fraction) affected (reduced or increased) by treatment with TNF antagonists? Is there a different effect compared to alternative therapy?
- ii) If microvascular dysfunction and/or inflammation are present before treatment, do they improve with treatment with TNF compared to alternative treatment? If parameters improve only with TNF inhibitor, this would suggest that TNF inhibitors exert a local anti-inflammatory effect on the myocardium mechanistically different compared to alternative treatment.
- iii) If treatment-induced improvements in microvascular dysfunction and/or inflammation (F18-FDG uptake) are

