observed with TNF inhibitor treatment and not with alternative treatment, do they correlate with (or mediate) global (or regional) changes in LV structure or function? If so, this would suggest a causal relationship between regional myocardial vasculopathy and/or inflammation with LV dysfunction.

iv) Do treatment-induced improvements in systemic inflammation (e.g., CRP) and RA disease activity correlate with changes in myocardial microvascular perfusion and/or inflammation? If so, this would suggest a relationship between systemic and myocardial inflammation.

In preliminary exploratory data analyses, summary statistics for the continuous and categorical variables will be calculated, including means, standard deviations, quartiles and ranges, and for the categorical variables, counts and percentages. In initial analyses, statistical comparison of continuous variables will be conducted using the t-test or nonparametric method, as appropriate. The comparisons of the prevalence of categorical CV risk factors will be conducted using the Chi-square test or the Fisher's exact test, as appropriate. All comparisons will be conducted at the  $\alpha=0.05$  level of significance using two-tailed tests, unless otherwise noted. To account for the potential for multiple comparisons artifact: a) First, significance testing will be based on a priori hypotheses and not spurious significant p-values; b) Second, if multiple comparisons are undertaken, adjustments in the threshold for statistical significance will be made as necessary. If multiple and collinear variables are detected, appropriate techniques will be utilized to minimize the impact of collinearity on the statistical efficiency of the derived parameter estimates.

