Linear mixed effects (MIXED) regression models will be used to assess trends in LV structure and functional outcomes over time between the two visits for the patients who will undergo randomization reevaluation with PET-CT and 3D Echocardiogram, while controlling for potential confounders. The data will include PET-CT studies for 25 RA patients receiving TNF antagonists and 25 RA patients receiving alternative treatment, and PET-CT studies for 15 non-RA patients. The data are longitudinal since LV outcomes are measured for each person at 2 different time points. Since repeated measures tend to be correlated within a person, mixed models with both fixed and random effects will be used to adjust for this correlation. We will use unstructured correlation structure given that each visit will occur roughly around a fixed time since study visit I, and use robust standard error estimates to conduct statistical inferences. To study the TNF inhibitor effects on LV structure or functional outcomes, visit-specific indicators, RA status, TNF treatment status, and visit x TNF treatment interaction will form the bases for the mean model. The visit-specific indicators will capture the time trend of LV outcomes over the study period, the RA status will delineate the overall mean difference in LV outcomes between RA and non-RA, with the TNF treatment status indicator and its interaction with visit indicators capturing the baseline difference in LV outcomes between TNF treated and non-treated groups and the potential TNF treatment effect on LV outcome over time, respectively. Actual TNF inhibitor dosage could be used in place of TNF status indicator in the model if necessary, and other potential covariates could be added into the model for confounding adjustment. For example, inflammation markers could be added into the model to examine whether any TNF treatment effect is mediated through the change in systemic inflammation. Similar modeling approaches can be used to study all research questions of interest using the corresponding outcomes and their hypothesized predictors listed in those questions to be addressed. For any binary outcomes in this type of regression analysis, e.g. indicator of whether a LV outcome exceeding certain critical value, generalized linear mixed effects models (GLIMMIX) can be used to study the odds of such outcome as a function of the independent variables.

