All analyses will be performed with STATA statistical software, version 9.0 (STATA Corp, College Station, TX) and PLINK (<http://pngu.mgh.harvard.edu/~purcell/plink>). In all tests, a two-tailed alpha error of 0.05 will be defined as the level of statistical significance.

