We will obtain valuable information on LV structure/function outcomes for the cross-sectional visit, as well as for change in these outcomes over 6 months, for 3 groups of study participants, 25 RA patients treated with TNF-antagonist, 25 RA patients treated with triple treatment or alternative, and 15 non-RA participants with otherwise similar characteristics. For continuous outcomes we will obtain mean, standard deviations, and skewness (to inform us whether certain variables may need transformation before analyses so that sample size/power evaluation for future studies may need to be based on transformed data) for cross-sectional as well as the change over time measurements, and the correlations between two consecutive measurements over time. For binary variables we will obtain prevalence estimates and odds ratios as estimates of association between two repeated binary measures over time. Even accounting for a possible 15% drop out rate of participants, the correlation estimate will have precision ranged approximately between within +/- 0.33 for a correlation of 0.50 and within +/- 0.09 for a correlation of 0.90. For prevalence of binary outcomes, our estimate will be ranged approximately from within +/- 17.9% for a prevalence of 50% to +/-10.7% for a prevalence of 90%. To estimate the power of detecting a 24 week (6 month) change in an LV myocardial outcome within the TNF treated RA group, with a 2-sided alpha of 0.05 and N=22 (accounting for possible drop out), we calculated the minimal detectable change based on cross-sectional SDs and various values for within person correlation between outcome measures at subsequent visits based on data from previous studies performed by the same investigator group. For example with a conservative SD of 1.8 L/min for cardiac output (CO) and 4.2 mL/m^2 for stroke volume (SV) and the correlation between subsequent visits being 0.2 we will have 80% power to detect a 24 week (6 month) change of 1.47 l/min for CO or 3.42 ml/m^2 for SV or more in the TNF inhibitor treated RA group. Similarly in order to estimate power for comparing changes between the TNF inhibitor treated group, the triple therapy treated group and the normal control group we based our calculations with comparing the changes between those groups with one way ANOVA assuming a 15% drop out and a 2-sided alpha of 0.05. We will have 80% power to detect any set of 3 group differences/changes if the SD of the changes is 0.444 or greater. We will have 80% power to detect a difference through the 3 group-one-way-ANOVA if the mean 24 week (6 month) change in SV for the TNF inhibitor group is 5.2ml/m^2 or higher while the mean change for the other two groups is 0. To provide a context regarding the number used above as an expected change in SV we would like to mention here that in our pilot data we observed a change in SV of 12.5mL/m^2 or higher with TNF inhibitor treatment in patients with RA.

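### Aim 2 question iii reads correlated changes in perfusion/FDG uptake and LV outcomes as causal, which two outcomes measured at the same two visits cannot support; the analysis behind it is also not fixed

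*Combined protocol and SAP*

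**What the plan says.** Section 2a lists the aim 2 questions with the words "For the 50 patients undergoing randomization and the controls the questions to be addressed will be the following". Question iii applies if microvascular dysfunction or FDG uptake improves with TNF inhibitor and not with the alternative. It then asks: "do they correlate with (or mediate) global (or regional) changes in LV structure or function". A positive answer is read as follows: "If so, this would suggest a causal relationship between regional myocardial vasculopathy and/or inflammation with LV dysfunction".

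Question iv asks: "Do treatment-induced improvements in systemic inflammation (e.g., CRP) and RA disease activity correlate with changes in myocardial microvascular perfusion and/or inflammation". Its reading is weaker: "If so, this would suggest a relationship between systemic and myocardial inflammation". It does not use the word causal.

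The mixed-model paragraph of section 2a plans for "25 RA patients receiving TNF antagonists and 25 RA patients receiving alternative treatment", plus 15 non-RA controls. Its mean model has visit, RA status, TNF status and visit x TNF. It allows similar models for all the research questions and offers, as an option, adding inflammation markers to examine mediation through systemic inflammation. For questions iii and iv the section does not fix the estimator, the analysis set or the adjustment for arm, and it gives no assumptions for a mediation or causal reading. The significance rule is general: "In all tests, a two-tailed alpha error of 0.05 will be defined as the level of statistical significance".

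**The concern.** Question iii is asked precisely when the two arms differ in the change in perfusion or FDG uptake. If TNF inhibition also moves an LV outcome, by whatever route, the TNF arm lies higher on both changes and the other arm lower on both. A correlation over the two arms is then non-zero even if, within each arm, a patient's perfusion change says nothing about that patient's LV change.

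Removing the arm means removes this artefact but still does not make the result causal. The two changes span the same 24 weeks, so direction cannot be established, and anything that makes some patients respond on both measures produces a correlation without one outcome driving the other.

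At stake is the main mechanistic claim of aim 2, that local vasculopathy or inflammation drives LV dysfunction. Under the stated rule it could be reached when TNF inhibition merely acts on each outcome separately.

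**Working it through.** **The plan's own figures.** Section 2b gives no power or error rate for questions iii and iv. Its nearest figure is 80% power for a correlation of 0.227 with N = 150, two-sided 0.05. By Fisher z: atanh(0.227) x sqrt(147) - 1.96 = 0.84, and Phi(0.84) = 80.0%. This reproduces.

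**Shifts in SD of change**, using SD of change = SD x sqrt(2(1 - r)):

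- LV mass (section 2b: SD 27 g, r = 0.35, difference 27 g): 27 x sqrt(1.30) = 30.8 g, so d = 27/30.8 = 0.88. With 25 per arm, two-sided, power is 86.0%, in line with the stated more than 85%.
- Stroke volume (section 2b: SD 4.2, r = 0.2, difference 5.2 mL/m2): 4.2 x sqrt(1.60) = 5.31, so d = 5.2/5.31 = 0.98. With r = 0.2 the three-group ANOVA has 87-89% power rather than the stated 80%; the figure is used here only for the size of the shift.
- FDG uptake: a 50% decrease, with no SD. The stated power of more than 80% suggests roughly 0.8-0.9 SD or more, but this is an assumption. No shift is given for perfusion.

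**Completers.** Section 2b: "Even accounting for a possible 15% drop out rate of participants". This leaves 21 or 22 per arm, and about 13 controls.

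**Pooled correlation with no link within arm.** With 1:1 allocation and shifts d1 and d2 in the TNF arm only,

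r = (d1 d2/4) / sqrt[(1 + d1²/4)(1 + d2²/4)].

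- d1 = d2 = 0.88: r = 0.1936/1.1936 = 0.162. With N = 44, atanh(0.162) x sqrt(41) = 1.05, and the two-sided rejection rate is 18%.
- d1 = d2 = 0.98: r = 0.2401/1.2401 = 0.194. With N = 44 the rate is 24%.

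**Simulated share of positive results, two unlinked changes, nominal 5%:**

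| Shift in both outcomes | Pooled, 22 per arm | Pooled, 25 per arm | Arm in the model |
|---|---|---|---|
| 0.5 SD | 6.6% | 7.0% | about 5% |
| 0.7 SD | 11.2% | 11.8% | about 5% |
| 0.88 SD | 18.3% | 20.9% | about 5% |
| 0.98 SD | 24.9% | 27.7% | about 5% |

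With 21 per arm the rates at 0.88 and 0.98 SD are about 17-18% and 24-25%; adding 13 controls to the pool raises them to about 20-21% and 27-28%. Unequal shifts of 0.8 and 0.3 SD give 6.6% at 22 per arm. Counting only trials in which the first outcome improved with TNF and not with the alternative changes little (18.5% at 0.88 SD).

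**Question iv with controls included.** The mean model has visit x TNF but no visit x RA term. On the change scale, triple-therapy patients and controls therefore share one mean. Suppose both RA arms (21 + 21) improve on two unlinked measures and 13 controls do not. Adjusting for TNF status alone gives 12% positives at 0.88 SD and 16% at 1.0 SD. A separate mean for each of the three groups returns about 5%.

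**What arm adjustment leaves.** If a shared patient-level cause gives a within-arm correlation of 0.2 (assumed), it is significant in 14% of trials in the TNF arm alone (n = 22) and in 25% with both arms, adjusted (N = 44).

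**The case against.** The strongest defence is that the plan never prescribes a raw pooled correlation. The base model contains TNF status and visit x TNF, and the text says similar models can serve every question. Applied to question iii, that model gives about 5%, even with controls included. The wording of iii also reads naturally as confined to patients improving on TNF inhibitor, where a uniform shift creates no correlation. It mentions mediation, so correlation is not the only analysis foreseen. For iv, controls receive no treatment and so have no treatment-induced improvement, and section 2a already assigns them the role of showing normal variation.

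Much of this stands. A reader might infer that the plan commits to a test with two to five times its nominal error. The documents do not support that: pooling is one analysis left open, and the range needs shifts of about 0.7-1.0 SD in both outcomes. Nor is it type I error, since under parallel effects the pooled correlation really is non-zero and rejecting is correct for that test. A reader might also infer that iv draws a causal conclusion; it does not.

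A mixture of responders in the TNF arm is a tempting further proof. With n = 21, 50-70% responders improving by 1.5 SD on both outcomes gives 30-38% positives, but only if the same patients respond on both, which is itself a patient-level link. With independent responder status the rate is about 5%. The example shows only that a within-arm correlation need not be causal.

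The defence does not rescue the inference rule. The modelling text is permissive, its one mediator example is systemic inflammation rather than the path from perfusion or FDG uptake to LV function, and neither a within-arm nor an arm-adjusted correlation supports a causal reading.

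**Conclusion.** Wrong as written, for the causal inference rule in question iii. Correlated changes over the same interval cannot show that vasculopathy or inflammation drives LV dysfunction, however the correlation is computed.

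The size depends on the analysis, which the plan leaves open. Without an arm term, parallel unlinked effects of 0.88-0.98 SD give about 17-25% positive results with 21 or 22 per arm; at 0.5 SD the excess almost disappears. The LV shifts follow from the plan's own figures; an equal shift in FDG uptake or perfusion is assumed. With arm in the model the artefact is gone, but a shared patient-level response remains.

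For question iv the point is narrower: if controls are included and only TNF status is adjusted for, about 16% positives arise when both RA arms improve by 1 SD on unlinked measures.

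**What to change.** In section 2a, for questions iii and iv:

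1. Specify a regression of change on change in the randomised RA patients only, with arm as a covariate, and report the slope with its 95% CI. Use the controls only to describe normal variation over 24 weeks.
2. In question iii, replace the causal conclusion with: *would suggest an association between changes within treatment arm*. Add that direction and mediation cannot be inferred from two simultaneous visits, because arm adjustment does not remove a shared patient-level response.

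The cost is one model term, a few sentences and a weaker stated conclusion. No new data or visits are needed.

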
Based on preliminary data RA patients had an LV mass of 120± 27 grams while normal people had an LV mass of 147

$\pm 40$  gram. For a change in left ventricle mass from 120 to 147 grams over the 6 month period we will have an 80% power to detect this improvement of LV mass in 25 patients treated with TNF inhibitor with a one sided alpha of 0.05 assuming a correlation of 0.35. We will have more than 85% power to detect a difference of 27 grams of mass between the TNF inhibitor treated group and the triple therapy treated group.

For changes in FDG uptake indicative of myocardial inflammation we assume that according to AHA guidelines a significant change in the intensity of FDG uptake would be equal to a decrease of 50%. We will have more than 80% power to detect such a difference between the TNF inhibitor treated group and the triple therapy treated group after 6 months of treatment with a 2 sided alpha of 0.05.

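### The aim 2 mixed model names robust standard errors without a small-sample correction; in the ordinary form the two-sided error is about 6% rather than 5%

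*Combined protocol and SAP*

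**What the plan says.** Section 2a describes one longitudinal model for aim 2.

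- Variance estimation: the analysts will "use robust standard error estimates to conduct statistical inferences".
- Covariance: "We will use unstructured correlation structure given that each visit will occur roughly around a fixed time since study visit I". There are two visits, so this is a 2x2 matrix.
- Mean model: "visit-specific indicators, RA status, TNF treatment status, and visit x TNF treatment interaction will form the bases for the mean model".
- Data: "The data will include PET-CT studies for 25 RA patients receiving TNF antagonists and 25 RA patients receiving alternative treatment", plus 15 people without RA.
- Error level, at the end of section 2a: "In all tests, a two-tailed alpha error of 0.05 will be defined as the level of statistical significance".

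Section 2b begins its precision statement with "Even accounting for a possible 15% drop out rate of participants" and gives "N=22 (accounting for possible drop out" for the within-TNF-arm calculation. No section says which form of robust standard error is meant, what reference distribution the tests use, or how degrees of freedom are found.

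**The concern.** The sandwich estimator builds the variance from squared residuals. Residuals from a fitted model are on average smaller than the true errors, so in small samples the uncorrected estimator is biased downward. It is also often paired with a normal reference, which ignores that the variance was estimated from few people. Both faults push the same way: rejection rates above nominal and intervals that are too short. With about 21 people per randomised arm, neither is negligible.

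Section 2a extends similar modelling to all research questions, so any excess recurs across many LV, perfusion and FDG outcomes. The same section plans t-tests for initial comparisons. The same arm contrast could therefore be judged by two slightly different standards, and a borderline result could reach significance only in the model.

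**Working it through.** **Inputs.** Two-sided alpha of 0.05 and the mean and covariance model: section 2a. Group sizes 25/25/15: sections 2a and 2b. Dropout of 15%: section 2b, giving 25 × 0.85 = 21.25 per RA arm and 15 × 0.85 = 12.75 controls; the plan itself uses 22 for the TNF arm. LV mass SD of 27 g and correlation of 0.35: section 2b.

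**The plan's own figure.** Section 2b claims more than 85% power for a 27 g difference between arms. Taking the 0.35 correlation and a two-sided 0.05 test to apply to that sentence:

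- SD of change = 27 × √(2 × (1 − 0.35)) = 30.8 g.
- Standard error with 25 per arm = 30.8 × √(2/25) = 8.71 g, and 27/8.71 = 3.10.
- Power is 87.3% with a normal reference and 86.0% with a t reference.

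The claim reproduces without dropout. At 21 per arm the figures are 81.1% and 79.2%. The change contrast between arms is therefore the right quantity to examine.

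**Closed form for two complete arms of n.** The uncorrected sandwich variance of the difference in mean change is (n − 1)/n times the unbiased one. With equal variances and a normal reference, the true error is P(|t| > 1.96 × √((n − 1)/n)) on 2n − 2 degrees of freedom.

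| n per arm | effective cut-off | correct t cut-off | true error | interval too narrow by |
|---|---|---|---|---|
| 21 | 1.913 | 2.021 | 6.3% | 5.4% |
| 22 | 1.915 | 2.018 | 6.2% | 5.1% |
| 25 | 1.920 | 2.011 | 6.1% | 4.5% |

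At 21 per arm:

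- The correct interval is 2.021/1.913 = 1.057 times as wide, and coverage of the nominal 95% interval is about 93.7%.
- An unbiased standard error with a normal reference gives 5.7%.
- The uncorrected sandwich with a t reference gives P(|t| > 2.021 × √(20/21)) on 40 df = 5.6%.

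The reference distribution and the sandwich bias thus contribute in similar measure.

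**Within-arm change.** The same formula for one arm, on n − 1 degrees of freedom, gives 7.0% at 21 and 6.9% at 22. The interval at 21 is 8.3% narrower than exact (1.913/2.086 = 0.917).

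**Simulation of the section 2a model.** Maximum likelihood, unstructured 2x2 covariance, 20,000 runs per scenario, Monte Carlo standard error about 0.17 percentage points. Error of the visit × TNF test with uncorrected robust errors and a normal reference:

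- RA arms only, 21/21: 6.2%
- planned model, 21/21/13: 6.4%
- planned model, 25/25/15, 15% missing Visit II: 6.3%
- the same with a visit × RA term added: 6.2%
- the same with four covariates: 6.1%
- the same with the TNF-arm SD 1.5 times larger: 6.3%
- the same with skewed (lognormal) data: 6.0%

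A t reference without a corrected standard error gave 5.4% to 5.9% across the scenarios. A Mancl-DeRouen corrected sandwich with a t reference gave 4.4% to 4.9%.

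**The case against.** The strongest reply is that the documents never say uncorrected, and never say normal reference. Both are read from silence. If the analysts use a corrected sandwich with a t reference, the excess disappears. This stands, and it makes the point a request for specification rather than proof of an error.

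The second reply is that robust errors are the wrong target. Model-based maximum-likelihood errors with a normal reference gave 5.8% to 6.4% in the equal-variance scenarios, so the excess is not special to the sandwich. This also stands.

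A reader might go further and infer that the sandwich adds only noise, since an unstructured covariance is already flexible, and that the plan should switch to model-based errors. The documents do not support that. A single unstructured matrix lets variances differ between visits, not between groups, and section 2b itself reports different LV mass SDs: "RA patients had an LV mass of 120± 27 grams" against ± 40 g in normal people. With the TNF-arm SD assumed 1.5 times larger, model-based errors with a normal reference gave 8.4%, against 6.3% for robust errors. In a complete-data change-score approximation, a pooled-variance t test gave about 7.3% to 7.4% in that case. The pooled test fell to 4.0% when the control SD was scaled by 40/27, where a corrected robust t test gave 5.0%. The robust choice is defensible and should stay.

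Finally, an excess of about one percentage point is unlikely to change the conclusions of a mechanistic study of 25 per arm. That is fair, and it sets the priority of the point.

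**Conclusion.** The point holds as a minor one. Read in its ordinary form, the section 2a model does not secure the plan's own 5% level. The between-arm error is about 6.0% to 6.4%, or about 5.6% with a t reference alone, and its 95% intervals are about 5% too narrow. A within-TNF-arm change test has about 7% error.

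Two larger readings are not supported.

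- A reader might infer that covariate adjustment takes the error to 9% or 10%. A change-score regression with uncorrected errors and 5 to 8 covariates would give 8.7% to 10.2%, but the plan specifies no such regression and no number of covariates. The planned model with four covariates gave 6.1%.
- A reader might infer that every aim 2 interval is affected. The t-tests in section 2a and the one-way ANOVA in section 2b do not use the sandwich. Only results from the mixed model are concerned.

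The figures assume an uncorrected sandwich, a normal reference unless stated otherwise, and dropout completely at random. The 1.5-fold SD ratio, the lognormal shape and the four independent covariates are assumptions not taken from the documents. The stated mean model has no visit × RA term, so the visit × TNF contrast pools controls with triple therapy; adding the term hardly changed the error.

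**What to change.** In section 2a, keep the robust standard errors and state three things: a small-sample-corrected form (for example Mancl-DeRouen, or an HC2- or HC3-type correction), a t reference, and the method for its degrees of freedom. Apply the same rule to within-arm changes estimated from this model.

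The cost is wording only. Between-arm intervals become about 5% to 6% wider if the correction restores the unbiased variance (1.057 times at 21 per arm, 1.047 times at 25). Mancl-DeRouen and HC3-type corrections overshoot slightly. For two complete arms of 21 their variance is 21/20 of the unbiased one, so the interval is 2.021 × √(21/20)/1.913 = 1.08 times the uncorrected width, in line with the 4.4% to 4.9% error seen in simulation. Within-arm intervals at 21 patients become about 9% wider (2.086/1.913 = 1.09) under a correction that restores the unbiased variance.
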